8.7 Safety analyses

The following assessments will be used to evaluate the overall safety of CR845:

- Adverse events
- Vital signs
- 12-lead ECGs
- Clinical laboratory evaluations.

All safety analysis will be performed using the safety population. All safety endpoints will be summarized by treatment group and overall. Baseline value defined as the last lab value obtained prior to treatment.

Statistical Analysis Plan (SAP)

8.7.1 Adverse events

All adverse events (AE) will be coded using MedDRA dictionary to the corresponding MedDRA system organ class (SOC) and Preferred Term (PT) for standardization and summary purposes. Only treatment emergent adverse events (TEAEs) will be included in summary tables, except for a table presenting an overall summary of all AES and of REAEs. Summaries will provide results overall and by treatment.

TEAEs are defined as adverse events (AEs) with an onset date on or after the first dose of the study drug up to the End of Treatment/Early Termination visit or 7 days after the last dose, whichever is later.

The incidence of TEAEs will be presented using counts and percentages of patients with adverse events and tabulated by SOC and preferred term. System organ class will be sorted alphabetically and preferred term within SOC will be sorted by descending frequency based on the incidence across all patients in the safety population. A patient will be counted only once in the incidence count for a MedDRA SOC or preferred term, although a patient may have multiple occurrences (start and stop) of an event associated with a specific MedDRA preferred term or SOC.

The following specific summary tables will be generated:

- An overall summary showing the number and percentage of patients with
 - Any AE (both TEAE and non-TEAE)
 - TEAE
 - Serious TEAE
 - Serious non-TEAE
 - Related TEAE
 - Severe TEAE
 - TEAE leading to drug interruption
 - TEAE leading to dose reduction
 - TEAE leading to study drug discontinuation
 - Number of any events and number of TEAEs (Count only)
- TEAEs by SOC and preferred term
- TEAEs related to study drug by SOC and preferred term
- TEAEs by SOC, preferred term and maximum severity
- TEAEs occurring in $\geq 5\%$ of patients in at least 1 treatment group
- Treatment-related TEAEs occurring in $\geq 5\%$ of patients in at least 1 treatment group

Statistical Analysis Plan (SAP)

- Serious TEAEs by SOC and preferred term
- TEAEs leading to study drug discontinuation by SOC and preferred term

If the relationship to the study drug of an adverse event (AE) is missing, the AE will be categorized as “related” to the study drug. If a patient reports 2 or more AEs that code to the same preferred term, the event with the maximum relationship will be included in the table.

If the severity to the study drug of an AE is missing, the AE will be categorized as “severe”. If a patient reports 2 or more adverse events that code to the same preferred term, the event with the maximum severity will be included in the table.

All adverse events will be listed in chronological order, including patient identifier, age, race, gender, a flag indicating whether the event was treatment-emergent, and all related event status information (start and stop dates, whether the event was ongoing, study day of onset, severity, seriousness, relationship to study drug, action taken with study drug, and outcome).

In addition, separate listings will be generated for serious adverse events (SAEs), deaths, and adverse events leading to study drug discontinuation.

A coding list of SOC, high level, preferred and lowest level terms and the verbatim text associated with them will also be produced additionally. TEAEs and non-TEAEs will be listed separately.

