6.5.2.1 Adverse Events

6.5.2.1.1 Definition of Adverse Event

An adverse event is any untoward medical occurrence in a patient or clinical investigation subject administered a medicinal product and that does not necessarily have to have a causal relationship with this treatment. An adverse event can therefore be any unfavorable and unintended sign (including an abnormal laboratory finding, for example), symptom, or disease temporally associated with the use of a medicinal product, whether or not considered related to the medicinal product.

In this study, adverse events will be captured from the time a patient signs the ICF to the Follow-up Visit and include the following:

- Any new sign, symptom, or disease;
- Any new clinically significant or symptomatic laboratory/diagnostic test abnormality;
- Any clinically significant worsening of laboratory/diagnostic test abnormality;
- Any worsening (ie, clinically significant change in frequency, nature and/or intensity) of a pre-existing condition.

A pre-existing condition is a condition that is present prior to signing the ICF for the study. Pre-existing conditions, such as illnesses, symptoms, reactions, progression of disease states, and other comorbidities, as well as pre-existing laboratory/diagnostic test abnormalities, will be documented in the patient's record as medical history.

Signs and symptoms will be reported individually as adverse events (non-serious), unless a medical diagnosis was provided. Medical diagnosis, whenever provided, will be reported rather than individual signs and symptoms.

Any adverse event that satisfies any of the seriousness criteria described in [Section 6.5.2.1.3](#) will be reported as a serious adverse event (SAE) using the SAE Report Form, in addition to documenting in the eCRF.

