6.5.2.1.6 Adverse Event Documentation and Follow-up

All adverse events, including observed, elicited, or volunteered problems, complaints, or symptoms are to be recorded on the adverse event page in the patient’s eCRF from the time the patient signs the ICF until the Follow-up Visit/early termination, whether or not judged by the Investigator to be related to study drug. The need to capture this information is not dependent upon whether adverse events are related to study drug. Serious adverse events that occurred up to 30 days after the last dose of study drug need to be documented on an SAE Report Form if they are deemed by the Investigator to be “Related” to study drug.

Each adverse event is to be documented with a verbatim/reported term, start and stop date, severity, causal relationship to study drug, action taken with study drug, and outcome (resolved, resolved with sequelae, resolving, not resolved, fatal, unknown). The Investigator must review new adverse events and the outcome of ongoing adverse events frequently throughout the study.

In addition to recording all adverse events (serious and non-serious) in the patient’s eCRF, all SAEs must also be documented on the SAE Report Form for the study.

The Investigator will follow all adverse events until they resolve, the Investigator assesses them to be stable, or the patient’s participation in the study ends, whichever comes first. In addition, the Investigator will follow all adverse events assessed as related to study drug that are ongoing at the time of the patient’s last visit, until they resolve or the Investigator assesses them as stable, even if the patient’s participation in the study has ended. Resolution of such events is to be documented in the patient’s record as appropriate.

It is anticipated that some patients may undergo procedures and/or experience events that are common in the study population under investigation, independent of study therapy. Preplanned procedures and procedures (eg, kidney transplant or catheter replacement) or events that are independent of study therapy, according to the Investigator’s assessment, will be documented as specified in the Safety Management Plan.

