8.7.2 Adverse Events

All adverse events will be coded using MedDRA dictionary to the corresponding MedDRA SOC and Preferred Term for standardization and summary purposes.

All reported adverse events (whether or not treatment-emergent) will be included in a by-patient adverse event listing. Only TEAEs will be included in summary tables.

Adverse events that are considered “treatment emergent” relative to the Run-in Period are identified as any adverse event with an onset date after the start of the Run-in Period and up to the first dose of study drug during the Treatment Period.

Adverse events that are considered “treatment emergent” relative to the Treatment Period are identified as any adverse event with an onset date after the first dose of the study drug up to the study End of Treatment/Early Termination Visit (or 7 to 10 days after the last dose if no End of Treatment/Early Termination Visit was conducted), whichever is later.

Treatment-emergent adverse events will be summarized by treatment group and by period (Run-in Period vs Treatment Period). The incidence of TEAEs will be presented using counts and percentages of patients with adverse events and tabulated by SOC and Preferred Term. System Organ Class will be sorted alphabetically and Preferred Term within SOC will be sorted by descending frequency based on the incidence across patients overall. A patient will be counted only once in the incidence count for a MedDRA SOC or Preferred Term, although a patient may have multiple occurrences (start and stop) of an event associated with a specific MedDRA Preferred Term or SOC.

The following specific summary tables will be generated:

- Incidence of TEAEs
- Incidence of TEAEs related to study drug
 - If the relationship to the study drug of an adverse event is missing, a worst-case scenario will be assumed (ie, the adverse event will be categorized as “related” to the study drug). If a patient reports 2 or more adverse events that code to the same Preferred Term, the event with the maximum relationship will be included in the table.
- Incidence of TEAEs by maximum severity

- If the severity to the study drug of an adverse event is missing, a worst-case scenario will be assumed (ie, the adverse event will be categorized as “severe”). If a patient reports 2 or more adverse events that code to the same Preferred Term, the event with the maximum severity will be included in the table.

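### The treatment-emergent rule uses onset date only, so a symptom that starts between consent and first dose and worsens on study drug counts as non-treatment-emergent unless a site opens a new record

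*SAP*

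**What the plan says.** **Classification.** SAP 8.7.1 states: "TEAEs are defined as adverse events (AEs) with an onset date on or after the first dose of the study drug". The window closes at the later of the end-of-treatment or early termination visit and 7 days after the last dose. There is no clause for an event that starts earlier and gets worse. Protocol 8.7.2 words the Treatment Period rule similarly, as "any adverse event with an onset date after the first dose of the study drug". Under Protocol 8.1 the SAP governs where the two differ.

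**Collection.** Protocol 6.5.2.1.1 says that "adverse events will be captured from the time a patient signs the ICF to the Follow-up Visit". Screening takes place 7 to 28 days before randomization (Protocol 6.1), so there is a real interval in which a dated pre-dose event can arise.

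**Worsening.** The same section counts as an adverse event "Any worsening (ie, clinically significant change in frequency, nature and/or intensity) of a pre-existing condition", and separately counts clinically significant worsening of a laboratory or diagnostic abnormality. It limits the first route: "A pre-existing condition is a condition that is present prior to signing the ICF for the study". Protocol 6.5.2.4 makes ECG findings that worsen after first dose treatment-emergent.

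**Recording.** Protocol 6.5.2.1.6: "Each adverse event is to be documented with a verbatim/reported term, start and stop date, severity", together with causality, action taken and outcome. It does not say what to do when the severity of an open event rises.

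**Reporting.** SAP 8.7.1: "Only treatment emergent adverse events (TEAEs) will be included in summary tables", apart from one overall summary. That summary has a row for any adverse event, treatment-emergent or not, and a row for serious non-TEAEs.

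**The concern.** The two parts of the definition do not meet. Worsening starts a new event only if the condition was there before consent, while treatment emergence requires onset on or after first dose. A clinical symptom that starts in between meets neither condition. It is already an event, its onset is before dosing, and its later worsening has no onset of its own.

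Protocol 4.3 names tingling or numbness, dizziness, fatigue and somnolence as the most common events with CR845, with nausea and constipation as possible. These are clinical symptoms, which the laboratory and ECG routes do not reach. If the drug aggravates such a symptom, the aggravation belongs in the on-treatment incidence. Drug-induced aggravation would fall in the active arms, so leaving it out would tend to narrow the difference from placebo. Safety is a secondary objective, and the interim analysis may drop a dose judged unsafe or poorly tolerated (SAP 8.9), so the tables serve a decision.

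**Working it through.** The plan gives no figure to reproduce. The check follows each kind of on-drug worsening through the rules.

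1. **Symptom present before consent, worse on drug.** Protocol 6.5.2.1.1 makes the worsening an adverse event in its own right. Its onset is the date of worsening, after first dose, so it can be a TEAE under SAP 8.7.1. Covered.
2. **Laboratory or diagnostic abnormality, or ECG finding, worse on drug.** Covered by Protocol 6.5.2.1.1 and 6.5.2.4.
3. **Clinical symptom first appearing after consent and before first dose, worse on drug.** At first appearance it is a new symptom and is recorded with that start date. It is not pre-existing, because it began after consent. No rule in either document gives the worsening a new record or resets the onset. The onset precedes first dose, so under SAP 8.7.1 it is a non-TEAE. Not covered.

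The contrast between cases 1 and 3 is arbitrary. Nausea that began the day before consent and worsens on drug can be a TEAE; nausea that began the day after consent and worsens in the same way is not.

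Other rules that might close the gap:

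- *Missing start dates* (SAP 7.2.2) are treated as treatment-emergent. This does not help when the pre-dose date is known.
- *Day 1 onset.* The SAP rule includes the date of first dose, so if only dates are compared, a symptom starting on Day 1 before the tablet counts as a TEAE. This removes one day from the gap.
- *Run-in category.* Protocol 8.7.2 plans a separate summary of events that start in the run-in. It would show the event as a run-in onset, not as worsening on drug, and would not reach onsets earlier in screening. The SAP definition omits this category.

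Where a case 3 event appears under SAP 8.2, 8.7.1 and 8.9.2:

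| Display | Included? |
|---|---|
| TEAEs by SOC and preferred term | No |
| Related TEAEs; TEAEs by maximum severity | No |
| Serious TEAEs; TEAEs leading to discontinuation | No |
| Interim TEAE summaries | No |
| Overall summary: any-event row | Yes, without term or severity |
| Overall summary: serious non-TEAE row | Yes, if serious |
| Disposition: reason for stopping treatment | Yes, if treatment is stopped |
| Final and interim listings | Yes |

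**Scale of one patient.** With 60 per arm, 1/60 = 1.7 percentage points. The interim analysis takes 50-60% of 240, that is 120-144 patients or 30-36 per arm if evenly split, so one patient is 1/36 = 2.8 to 1/30 = 3.3 points. The threshold for the common-TEAE tables is 5% of 60 = 3 patients in an arm.

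**Number of patients.** The documents give no pre-dose event rate, so this cannot be estimated. As illustration only, assume that 10-20% of 240 patients have a pre-dose event and 5-10% of those worsen on treatment. The trial-wide total is then 240 × 0.10 × 0.05 = 1.2 to 240 × 0.20 × 0.10 = 4.8. Divided by four arms, this is 0.3 to 1.2 patients per arm, and that is the figure to compare with the threshold of 3. Neither percentage comes from the documents.

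**The case against.** A reader might infer three stronger statements. The documents do not support them.

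*Such an event never reaches any TEAE table.* That depends on how sites enter a change in severity. If a site closes the first record and opens another dated at the worsening, the existing onset rule already captures it. The eCRF and its completion instructions are not among the documents, and their absence here does not show that no such instruction exists. What stands is that neither the protocol nor the SAP requires it, so with up to 80 sites classification may vary with local habit.

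*The interim safety review does not see these events.* SAP 8.9.2.5 exempts its first display from the TEAE restriction. That display counts all adverse events, and the interim package also lists adverse events, deaths, serious events and events leading to discontinuation. Only the interim TEAE summaries lose the event. What stands is that the any-event row has no term or severity, and a listing gives no incidence by arm.

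*Background symptoms of CKD that worsen on drug are lost.* Those present before consent are pre-existing conditions, and their worsening is already an event. The gap is confined to symptoms that first appear between consent and first dose.

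Two further objections carry weight. Safety is summarized descriptively with no inferential statistics, and efficacy is untouched, so no test result changes. Also, a SAP clause alone may be impossible to apply: without a dated severity change, the fields in Protocol 6.5.2.1.6 cannot show when the event worsened. That is a reason to pair the clause with a recording instruction, not to leave the rule as it is.

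**Conclusion.** The concern holds in a limited form. As written, the rules class a clinical symptom that first appears between consent and first dose and worsens on study drug as non-treatment-emergent, unless a site opens a new record unprompted. The event is then missing from the TEAE tables by SOC and preferred term, relatedness, maximum severity, seriousness and discontinuation, and from the interim TEAE summaries. It is not lost from the any-event and serious non-TEAE rows, the disposition reasons or the listings.

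The number of patients is probably small and cannot be estimated from the documents. The conclusion rests on the text of the protocol and SAP and assumes that no unseen eCRF instruction already requires a new record. The change is still worth making: the rule misclassifies on-drug worsening, the dividing line is the date of consent, which has no bearing on drug effect, and the correction is cheap.

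**What to change.** In SAP 8.7.1, define a TEAE as an adverse event with onset on or after first dose, or with onset before first dose and an increase in severity or seriousness on or after first dose, with the same end of window in both cases. Bring Protocol 8.7.2 into line, or list the difference in SAP section 9.

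Add an adverse event recording instruction: when an open event worsens after first dose, open a new record dated at the worsening. The clause states the classification; the instruction supplies the date needed to apply it. For records entered before the instruction is issued, the clause can be applied only where a dated increase was captured.

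The cost is one SAP clause and one eCRF completion instruction. TEAE counts may rise slightly. No efficacy analysis or hypothesis test is affected.

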8.7.2 Clinical laboratory evaluations

Blood samples for clinical laboratory tests, including hematology, serum chemistry and serum pregnancy will be collected during screening and day 1 before study drug administration, on week 6 and week 12 (end of treatment).

All clinical laboratory data will be reported in Système International units.

Summary statistics for each scheduled time point measured and mean changes from baseline to each time point will be presented for hematology and serum chemistry laboratory results. The baseline value is defined as the last observation prior to or on the date of the first dose of study drug whether scheduled or unscheduled (see [section 7.1](#)).

Hematology and serum chemistry laboratory test results will be assigned as Low (L), Normal (N) or High (H) classification according to whether the value was below (L), within (N), or above (H) the laboratory parameter’s reference range.

Statistical Analysis Plan (SAP)

Comparisons will be based on 3×3 tables (shift tables) that, for a particular laboratory test, compare the baseline L/N/H classification to the highest and/or lowest L/N/H classification during the treatment period.

Clinically important laboratory values based on the below specified criteria will also be summarized.

- Alanine aminotransferase (ALT), aspartate aminotransferase (AST),
 - $>3 \times$ ULN
 - $>5 \times$ ULN
 - ALT $>3\times$ ULN or AST $>3\times$ ULN
- Alkaline phosphatase (ALP)
 - $>1.5 \times$ ULN
- Total Bilirubin (TBILI)
 - $>2 \times$ ULN
- AST and Total Bilirubin
 - AST $>3\times$ ULN and TBILI $>2\times$ ULN
- ALT and Total Bilirubin
 - ALT $>3\times$ ULN and TBILI $>2\times$ ULN
- AST or ALT and Total Bilirubin
 - AST or ALT $>3\times$ ULN and TBILI $>2\times$ ULN

A summary of treatment emergent sodium findings will also be provided, categorizing results into those <146 mmol/L, $146 - 150$ mmol/L, and >150 mmol/L at the 6 and 12 week assessments. An additional summary will present these categories for subjects over the full study period presenting the highest category attained (at any on-treatment assessment) and sustained (at any on-treatment assessment and all subsequent on-treatment assessments); this analysis will include both scheduled and unscheduled laboratory test results.

All clinical laboratory values will be presented in a listing. Additionally, ALT, AST, bilirubin, ALP and sodium will be presented in a separate listing, with values $>3 \times$ or $>5 \times$ ULN flagged for alanine aminotransferase and aspartate aminotransferase; $2 \times$ ULN flagged for total bilirubin, $1.5 \times$ ULN flagged for alkaline phosphatase and ≥ 146 mmol/L flagged for sodium. In each listing, all the data for the patient across the study will be presented for any parameter flagged post-baseline.

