4.3 Summary of Potential Risks and Benefits

The potential benefit of CR845 in alleviating the symptoms of pruritus associated with chronic kidney disease (CKD) in hemodialysis patients is predicated on its pharmacological class and evidence of its effectiveness in multiple animal models of pruritus and in two Phase 2 clinical studies with IV CR845 in hemodialysis patients experiencing moderate-to-severe pruritus (CR845-CLIN2005 Part B and CR845-CLIN2101).

In humans with normal renal function, CR845 has aquaesthetic effects that can result in dehydration and associated symptoms (eg, tachycardia) and hypernatremia if the fluid balance is not managed properly. However, these effects appear to be absent in the dialysis population, many of whom are anuric and all of whom have few functioning nephrons. These effects are also anticipated to be largely reduced in CKD patients stage III to IV not yet on dialysis.

Overall, tingling/numbness, dizziness, fatigue and/or drowsiness/somnolence have been the most common adverse events. Due to the potential adverse event of fatigue/drowsiness/somnolence, subjects should be cautioned about operating hazardous machinery or operating a motor vehicle.

Gastrointestinal dysfunction (abdominal discomfort, nausea, constipation) may be possible, as it has been frequently reported after oral tablet administration in normal healthy volunteers.

Tingling sensation or facial numbness has been reported shortly after administration of CR845. This effect is transient and does not appear to be a clinically significant issue.

While it has been demonstrated that CR845 has substantially less access to the CNS than previously tested kappa opioid agonists, adverse CNS effects of CR845 (eg, altered mental status) could still be considered a possibility (eg, hypothetically, in patients with impaired blood-brain barrier functioning).

A detailed summary of the potential risks and benefits of CR845 is provided in the [\[Investigator's Brochure\]](#). The Investigator must become familiar with all sections of the current Investigator's Brochure for CR845 before the start of the study.

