6.2.1 Inclusion Criteria

To be eligible for inclusion into the study, a patient must meet the following criteria:

1. Willing and able to provide written informed consent prior to participating in this study;
2. Able to communicate clearly with the Investigator and staff, able to understand the study procedures, and able and willing to comply with the study requirements;
3. Male or female 18 years of age or older;
4. CKD patients not currently maintained on hemodialysis with stage III, IV, or V disease (ie, moderate renal impairment with estimated glomerular filtration rate (GFR) ≥ 30 and < 60 mL/min/1.73 m² or severe renal impairment with estimated GFR < 30 mL/min/1.73 m²). For patients with severe CKD on hemodialysis, they must be receiving hemodialysis 3 times per week for at least 3 months prior to the start of screening;

Note 1: Patients who have received a renal organ transplant and who are at least 6 months post-transplant with an estimated GFR < 60 mL/min/1.73 m² may participate if clinically stable and are on maintenance immunosuppression.

Note 2: Severe CKD patients on hemodialysis who require an additional hemodialysis treatment to manage fluid overload may be enrolled as long as it is anticipated that no more than 1 such treatment will be required in any given week.

Note 3: Severe CKD patients on hemodialysis receiving in-home hemodialysis may participate as long as they have switched to in-center hemodialysis at least 2 weeks prior to screening and plan to remain on in-center hemodialysis for the duration of the study.

5. If female, is not pregnant or nursing during any period of the study;
6. If female:
 - a. is surgically sterile; or
 - b. has been amenorrheic for at least 1 year and over the age of 55 years; or

- c. has a negative serum pregnancy test at screening and agrees to use acceptable contraceptive measures (eg, hormonal contraceptives, barrier with spermicide, intrauterine device, vasectomized partner, or abstinence) from the time of informed consent until 7 days after the last dose of study drug.
- 7. If male, agrees not to donate sperm after the first dose of study drug until 7 days after the last dose of study drug and agrees to use a condom with spermicide or abstain from heterosexual intercourse during the study until 7 days after the last dose of study drug.
Note: No restrictions are required for a vasectomized male provided his vasectomy was performed ≥ 4 months prior to screening;

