8.9.2.5 Safety Analysis

The following summaries will be provided to evaluate the safety profile of CR845. Analysis details are provided in [section 8.7.1](#). Except for the first display listed below, only TEAE during treatment period will be summarized.

- Overall summary of Adverse Event
- AEs summary by SOC and PT
- AEs related to study drug by SOC and PT
- AEs leads to study drug discontinuation by SOC and PT
- AEs by Maximum severity
- Serious adverse event summary
- Summary of Clinically important laboratory values
- Summary of Sodium abnormal findings (<146 mmol/L, ≥ 146 mmol/L, ≤ 150 mmol/L, >150 mmol/L)

Line plot for the below parameters will also be provided.

- Change from baseline in selected Laboratory Tests over Time (hemoglobin, creatinine, GFR, albumin, phosphate, calcium, sodium)
- Blood Pressure Measurements (Systolic and diastolic blood pressure)
- Heart Rate Measurements

In addition, the following listings will also be provided to support safety data.

- Listing of Adverse Events
- Listing of death
- Listing of Serious Adverse Events
- AEs leading to study drug discontinuation
- Listings for clinically important laboratory values

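### SAP 8.7.2 sets no on-treatment category for GFR or creatinine, and its low/normal/high shift table cannot show further decline in non-dialysis patients who enter with eGFR below 60

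*SAP*

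**What the plan says.** Protocol 8.7.3 leaves the criteria for clinically important laboratory values to the SAP. SAP 8.7.2 takes this up: "Clinically important laboratory values based on the below specified criteria will also be summarized". The list that follows covers ALT, AST, alkaline phosphatase and total bilirubin, alone or combined. Sodium has its own categories, both attained and sustained. The flagged listing has the same scope: "Additionally, ALT, AST, bilirubin, ALP and sodium will be presented in a separate listing".

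For other hematology and chemistry tests, including creatinine, two displays remain. One is continuous: "Summary statistics for each scheduled time point measured and mean changes from baseline to each time point will be presented". The other is a 3×3 table of low, normal and high against the reference range, which will "compare the baseline L/N/H classification to the highest and/or lowest L/N/H classification during the treatment period".

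Protocol 6.2.1, criterion 4, admits non-dialysis patients in two groups. The moderate group is defined by "moderate renal impairment with estimated glomerular filtration rate (GFR) ≥ 30 and < 60 mL/min/1.73 m²"; in the severe group eGFR is under 30. GFR is grouped in SAP 8.4.2 at baseline (two groups) and for patients who fail criterion 4 (five bands), but nowhere on treatment. SAP 8.8.1 limits safety by renal stratum to adverse events.

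The interim package (SAP 8.9.2.5) includes the clinically important laboratory values, a sodium summary, adverse event tables, and line plots of change from baseline in several tests, creatinine and GFR among them.

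**The concern.** A shift table against the reference range works when most patients start inside it. Here entry requires abnormal kidney function, so the table has almost no room to record worsening in the organ system that defines the population. The dialysis stratum is capped at about 20%, so about 80% or more of patients have residual function to lose, and transplant recipients may enter.

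The SAP gives per-patient counts for sodium and for vital signs, and it treats GFR and creatinine as worth plotting at the interim, yet it gives neither a per-patient count. At stake is whether a reader can see, arm by arm, how many patients lost a material share of kidney function. That matters most at the interim, where doses found unsafe or poorly tolerated are to be dropped.

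**Working it through.** The plan states no figure on this point, so there is none to reproduce. The documents give no laboratory reference range, baseline eGFR distribution or SD of change; these are assumed below.

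**1. What the low/normal/high table can show for eGFR.**
- Inputs: entry eGFR 10 to 59.9, evenly spread (assumed); lower limit 60, 75 or 90 (assumed); proportional falls of 10% to 70%.
- Rule: a patient is low if eGFR is under the limit. With baseline under 60 and limit at least 60, baseline × (1 − fall) is also under the limit.
- Result: 0% change category for every fall and limit tried. The exception is a patient eligible at screening whose last pre-dose value is at or above the limit.
- Creatinine is the mirror image: high stays high. A patient with in-range creatinine at baseline could move from normal to high; the documents do not allow that number to be estimated.

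**2. What the SAP's own GFR bands would show.**
- Bands from SAP 8.4.2: <15, 15–29, 30–59. Baseline evenly spread from 15 to 60 (assumed).
- For a fall f, the patients who drop a band are those from 15 up to 15/(1 − f) and from 30 up to 30/(1 − f). Their share is [15f/(1 − f) + 30f/(1 − f)] / 45 = f/(1 − f), for f up to 0.5.
- f = 0.25: 33%. f = 0.30: 43%. f = 0.40: 67%. f = 0.50: 100%.
- Bands alone miss more than half of 30% falls, and a patient already under 15 cannot move. A percent-change category is needed as well.

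**3. What means show.**
- Non-dialysis patients per arm at the minimum size: 60 × 0.80 = 48, with the dialysis cap filled.
- Illustration (assumed): 10% of them lose 12 mL/min/1.73 m² (30 to 18). Mean shift = 0.10 × 12 = 1.2.
- SE of the between-arm difference = SD × √(2/48) = 0.82, 1.02, 1.22 for an assumed SD of change of 4, 5, 6. Ratio = 1.47, 1.18, 0.98.
- At the interim (50% of 240, so 30 per arm and 30 × 0.80 = 24 non-dialysis): SE = SD × √(2/24) = 1.15 and 1.73 for SD 4 and 6; ratio = 1.04 and 0.69. This applies there only if the line plots show arm means, which the SAP does not say.

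**4. What a count would show, with its own noise.**
- Baseline 30, so a 30% fall is 9 units. Chance of crossing at one assessment with no true change, normal errors: Φ(−9/4) = 1.2% for SD 4; Φ(−9/6) = 6.7% for SD 6. Of 48 placebo patients: 0.6 to 3.2.
- For any of two assessments, if independent: 48 × [1 − (1 − p)²] = 1.2 to 6.2.
- With 10% truly losing 12 units, their chance of crossing is Φ(3/4) = 77% for SD 4 and Φ(3/6) = 69% for SD 6. The arm's share is 0.10 × 0.773 + 0.90 × 0.0122 = 8.8%, or 0.10 × 0.691 + 0.90 × 0.0668 = 12.9%. Expected counts at one assessment: 4.2 against 0.6 (SD 4), or 6.2 against 3.2 (SD 6).
- Difference over SE, with SE = √[p₁(1 − p₁)/48 + p₀(1 − p₀)/48]: 0.076/0.044 = 1.7, or 0.062/0.060 = 1.0.

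**The case against.** The strongest reply is that renal decline has other ways to surface. Protocol 6.5.2.1.1 makes clinically significant worsening of a laboratory abnormality an adverse event, and these events are tabulated per patient and by renal stratum (SAP 8.7.1, 8.8.1). Descriptive statistics include the minimum and maximum, every laboratory value is listed, and the interim has creatinine and GFR plots. This stands: a reader might infer that kidney function is judged only by means and shift tables, and that is not so. But the adverse event route has no numeric threshold and depends on judgement at up to 80 sites, extremes do not say how many patients, the listing carries no renal flag, and the plots are specified for the interim only.

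A reader might also infer that the drug is expected to damage the kidney. The documents do not support that. Protocol 4.3 describes "effects that can result in dehydration and associated symptoms (eg, tachycardia) and hypernatremia if the fluid balance is not managed properly", but for people with normal renal function. It says these effects appear absent on dialysis and should be largely reduced in stage III to IV. It does not name renal decline as a drug effect, and Protocol 7.2 reports no clinically important laboratory findings in the earlier non-dialysis CKD study. The consequences it does name are partly covered by the sodium categories and the notable blood pressure and heart rate counts.

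Finally, a count is not free of noise. Step 4 shows its statistical contrast is only slightly better than that of means, and safety is descriptive in any case. The advantage is that a count shows how many patients declined materially. It is not a more powerful test.

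**Conclusion.** The gap is real but limited. No on-treatment category for GFR or creatinine is defined, and the shift table cannot register further eGFR decline in non-dialysis patients, or further creatinine rise in those already high. The eGFR part rests on a laboratory lower limit of 60 or more and a baseline value still under it. The size of the dilution in means (1.2 units, about 1.0 to 1.5 SE at 48 per arm) rests on an assumed 10% of patients losing 12 units and an SD of change of 4 to 6.

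It would go too far to say that a decline could appear in no laboratory category table: creatinine that is in range at baseline can still move to high. No efficacy conclusion is affected. The change is worth making because the planned category display is nearly blind in this population and the data for a better one are already collected.

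**What to change.** For the two non-dialysis strata, by arm and renal stratum, add to SAP 8.7.2 and to the interim package in 8.9.2.5:

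- a shift table from baseline to the lowest on-treatment value and to the last one, on the SAP's existing GFR bands (<15, 15–29, 30–59);
- the number and percentage of patients by percent fall in eGFR from baseline (for example, at least 30%) and by ratio of creatinine to baseline (for example, at least 1.5), at any on-treatment assessment and at the last one.

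State that the cut-points are for descriptive reporting only and are not treatment rules; the documents supply none, so the sponsor should choose and prespecify them. State also that counts are to be read against placebo, because some crossings occur by chance; the last-assessment count helps separate lasting from transient change. Leave out the dialysis stratum, where change in GFR means little.

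The cost is one or two extra tables from chemistry data already collected, with no new samples or visits, and some chance threshold crossings to interpret.
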